#### Sensitivity Analyses

Three sensitivity analyses will be performed for the primary efficacy endpoint:

- 1. MMRM with imputation
- 2. analysis of covariance (ANCOVA)
- 3. ANCOVA using LDL-C by PUC only

#### Sensitivity Analysis 1

The first sensitivity analysis will be performed in two steps. In the first step, missing data will be assumed missing not at random (MNAR). Missing data at Day 28 and 56 will be imputed using multiple imputation methodology in two steps. Initially, 25 data sets will be imputed for non-monotone missing values in the original dataset. In the second step the remaining monotone missing values will be imputed. Upon completion of the trial, if the percentage of cases with incomplete data is larger than initially anticipated then the number of imputations will be increased for the final analysis.

The variables for the imputation model will consist of LDL-C values from Baseline and Days 28 and 56. For each imputation dataset, the percent change from baseline to Day 56 will be analyzed using the MMRM model described above. The results from these 25 analyses will be combined using Rubin's method to construct the treatment estimates using the parameter estimates and associated standard errors. Similarly, the difference of the adjusted treatment means (the two doses of obicetrapib therapy – Placebo) will be presented with the associated standard error and 95% confidence interval. Randomly chosen seed numbers will be selected for the analysis and will be retained.

Example SAS code to create a dataset for non-monotone missing values is shown below:

Note: non-MONOTONE missing values TREATMENT = 0 (Placebo), 1 (5 mg obicetrapib), 2 (10 mg obicetrapib) LDLC BASE = LDL C Baseline value LDLC Day28 = LDL C value at Day 28 LDLC Day56 = LDL C value at Day 56 proc mi data=LDLC\_Wide seed=18032021 out=LDLC\_25MCMC nimpute=25; var TREATMENT LDLC base LDLC Day28 LDL Day56; mcmc impute=monotone chain=multiple; In the second step, the remaining monotone missing values will be imputed. Example SAS code to complete this step is shown below: \* MONOTONE missing values TREATMENT = 0 (Placebo), 1 (5 mg obicetrapib), 2 (10 mg obicetrapib) LDLC BASE = LDL C Baseline value LDLC\_Day28 = LDL\_C value at Day 28 LDLC Day56 = LDL C value at Day 56 proc mi data= LDLC\_25MCMC seed=810456 out= LDLC\_Mono nimpute=1 simple; monotone method=rea: var TREATMENT LDLC\_base LDLC\_Day28 LDL\_Day56; by \_Imputation\_; run; For each imputation dataset, the percent change from Baseline to Day 28 and Day 56 will be analyzed using similar MMRM approach. Then the parameter estimates will be combined using Rubin's method. Example SAS code to combine the parameter estimates is shown below: Note: MIANALYZE to combine imputations proc mianalyze parms(classvar=full)=mixLSM; class TREATMENT: modeleffects TREATMENT: ods output parameterestimates=mi\_LSM; proc mianalyze parms(classvar=full)=mixDIFF; class TREATMENT: modeleffects TREATMENT; ods output parameterestimates=minus\_mi\_DIFF; \* Sensitivity Analysis 2

In the second sensitivity analysis, the percent change from Day 1 to Day 56 in LDL-C, via approach 1, for the obicetrapib groups compared to the placebo group will be analyzed using an Analysis of Covariance (ANCOVA) model with fixed effects of treatment group and the Baseline LDL-C value as a continuous covariate. The least squares means, standard errors, and 2-sided 95% confidence intervals for each treatment group, for the pairwise comparisons of two obicetrapib will be provided. The treatment comparison will be performed using a 2-sided test at the  $\alpha$  = 0.05 level of significance. No imputation of missing data will be performed for this sensitivity analysis.

Example SAS code can be found below:

#### Sensitivity Analysis 3

In the final sensitivity analysis, the percent change from Day 1 to Day 56 in LDL-C will be assessed where the LDL-C values will be measured by PUC. The percent change from Day 1 to Day 56 in LDL-C by PUC for the obicetrapib groups compared to the placebo group will be analyzed using an ANCOVA similar to the model described in the second sensitivity analysis. No imputation of missing data will be performed for this sensitivity analysis.

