#### 6 PROGRAMMING SPECIFICATIONS

Analyses will be performed using SAS® version 9.4. All available data will be presented in participant data listings which will be sorted by participant and visit date as applicable. Detailed Programming Specifications will be provided in a separate document.

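### Sensitivity Analysis 1 is labelled missing not at random, but no such mechanism is specified, and its prose and code disagree on whether treatment is in the imputation model

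*SAP*

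**What the plan says.** SAP 3.4.1 gives the primary analysis as a mixed model for repeated measures (MMRM) on percent change at Days 28 and 56, under MAR and without imputation. Three sensitivity analyses follow. The first is listed as "MMRM with imputation", and its assumption is stated as "In the first step, missing data will be assumed missing not at random (MNAR". The text then describes 25 imputed data sets for non-monotone gaps, imputation of the remaining monotone gaps, the same MMRM on each data set, and pooling by Rubin's method.

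The imputation variables are given in prose: "The variables for the imputation model will consist of LDL-C values from Baseline and Days 28 and 56". The example code that follows has two PROC MI steps. The first reads "var TREATMENT LDLC base LDLC Day28 LDL Day56" and "mcmc impute=monotone chain=multiple". The second has the same variable list and "monotone method=rea", evidently the regression method with a character lost in text extraction. Treatment is coded "TREATMENT = 0 (Placebo), 1 (5 mg obicetrapib), 2 (10 mg obicetrapib".

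Sensitivity Analyses 2 and 3 are ANCOVAs without imputation. SAP 6 adds: "Detailed Programming Specifications will be provided in a separate document".

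**The concern.** An MNAR analysis has to say how unobserved values differ from what the observed data predict: by how much, or according to which reference arm or pattern. Neither the prose nor the visible code does so. Readers of the study report would take this analysis as evidence that the result survives informative dropout, although that was not examined.

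The second problem is reproducibility. One programmer following the prose and another following the code would fit different imputation models. The two models have different consequences for the contrasts, and neither consequence follows from a stated MNAR assumption.

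**Working it through.** **1. Label against method.** Both steps draw missing values from a model fitted to observed values, which is imputation under MAR. Reading the MNAR statement as covering only the first step does not rescue it. That step handles non-monotone gaps (for example Day 28 missing, Day 56 present). Ordinary dropout is monotone and falls to the second step, where nothing MNAR is claimed.

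**2. Other analyses.** Sensitivity Analyses 2 and 3 use observed values only. The supportive ITT analysis (SAP 3.4) cannot supply values that were never collected. The per-protocol set requires a Day 56 value. None tests departure from MAR.

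**3. The plan's own figures (SAP 2.2.4).** Effect 30 points, SD 15, 36 evaluable per arm, two-sided 0.025, 5% dropout.
- SE of a contrast = 15 × √(2/36) = 3.54. Then 30/3.54 = 8.5 against a critical value of about 2.24, so power exceeds 99.99%, consistent with the stated >90%.
- 36/0.95 = 37.9, so 38 per arm and 114 in total, as planned. Expected dropout is 0.05 × 38 = 1.9, about 2 per arm.

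**4. Effect of the treatment term.** Assumed, not in the documents: true effects of -30 in both doses, placebo change 0, and the same fraction p missing completely at random in each arm.

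*Both visits missing, treatment omitted.* Every missing value is drawn around the pooled mean, (0 - 30 - 30)/3 = -20, in all arms. The contrast is -30 × (1 - p).

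*Both visits missing, linear 0/1/2 score.* The fitted line has slope (-30 - 0)/2 = -15 through -20 at score 1, giving -5, -20 and -35. Imputed contrasts are -15 for 5 mg and -30 for 10 mg. The 5 mg contrast becomes -30 + 15p, and 10 mg is unchanged.

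| p | Omitted, both doses | Linear, 5 mg | Linear, 10 mg | Categorical |
|---|---|---|---|---|
| 5% | -28.5 | -29.25 | -30 | -30 |
| 10% | -27.0 | -28.5 | -30 | -30 |
| 20% | -24.0 | -27.0 | -30 | -30 |

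*Only Day 56 missing, treatment omitted.* Further assumptions: Day 28 effect -28, within-person correlation 0.6.
- Pooled slope of Day 56 on Day 28 = (0.6 × 225 + 28 × 30 × 2/9) / (225 + 28² × 2/9) = 321.7/399.2 = 0.806.
- Predicted contrast = 0.806 × 28 = 22.6, a shortfall of 7.4 per missing value. At 5% this is 0.37 points.

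**5. Simulation at trial size.** 38 per arm, 5% missing, 600 replicates, 10 imputations, effects -30/-30 unless stated. Assumed baseline: mean 95, SD 22, floored at 70. Assumed visit correlation: 0.5 or 0.7. Attenuation in points:
- Treatment omitted: 0.26 to 0.47 (Day 56 only), 0.88 to 0.98 (half of dropouts miss both visits), 1.51 to 1.55 (all miss both).
- Linear score: 5 mg 0.20 to 0.72 across the same patterns, 10 mg within 0.04 of zero.
- Linear score with true effects -15/-30 (correlation 0.5): 5 mg 0.00, 10 mg within 0.05 of zero.
- Categorical treatment: at most about 0.1 in size.

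**6. What a real MNAR shift would do.** With treatment categorical and a shift d added to imputed active-arm values, the estimate is -30 + p × d. At 5%, d = 0, 10, 20, 30 gives -30, -29.5, -29.0, -28.5.

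**The case against.** **The code is damaged and only an example.** This stands. Other example code announced in SAP 3.4.1 does not appear in the text available, and detailed specifications are held separately. A reader might infer that the code proves there is no MNAR or CLASS statement; it cannot. The MNAR point therefore rests on the prose, which is intact and names no mechanism. The linear-score point stays conditional.

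**Treatment is probably in the model.** The prose list might name only variables to be imputed, and both code steps include treatment. So omission is the less likely implementation. But the list also contains the baseline value, which every mITT participant has by definition, so it does not read as a list of incomplete variables. The texts still need to agree.

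**The 1.5-point figure is extreme.** This stands. Protocol 4.5 asks early discontinuers to complete the Early Termination assessments, Appendix A includes a lipid profile there, and SAP 3.1.2 maps that visit to Day 28 (days 2 to 42) or Day 56 (days 43 to 71). Most dropouts who attend would supply a post-baseline value, unless SAP 3.4.1 excludes it for prohibited medication or non-adherence.

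**Agreement with the MMRM is guaranteed.** A reader might infer this in every case. It holds only if treatment is modelled adequately. The prose version pools the arms, which the MMRM does not.

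**The pooled version is a conservative MNAR analysis in practice.** Its -28.5 equals the full-loss figure in step 6, but this is a coincidence of contrasts. Pooling gives placebo dropouts an imputed change of -20, two thirds of the drug effect. No stated assumption says that.

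**The protocol does not require an MNAR analysis.** True: protocol 9.2.1.2 leaves further sensitivity analyses to the SAP. Correcting the label is therefore a sufficient repair.

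**Conclusion.** The point holds. Sensitivity Analysis 1 claims an MNAR assumption that its prose does not specify and its visible code does not implement, and no other planned sensitivity analysis tests departure from MAR. The prose and code also conflict on the treatment term.

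The numerical consequences are small. At 5% missing and equal 30-point effects, omitting treatment costs about 0.3 to 0.5 points when only Day 56 is missing, and up to about 1.5 in the unlikely case that all dropouts miss both visits. A linear score would cost the 5 mg contrast about 0.2 to 0.7 points. Equal effects are an assumption, though protocol 5.2 reports near-maximal effects at 5 mg. If 10 mg had twice the effect of 5 mg, the linear score would cause no bias.

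A reader might infer that the primary result is in doubt. The documents do not support that: the primary MMRM uses no imputation, and these shifts are small beside a 30-point planned effect and an SE of about 3.5. The defect should be fixed because it would misdescribe what was tested.

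**What to change.** In SAP 3.4.1, Sensitivity Analysis 1:

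1. Choose one.
   - (a) Replace missing not at random (MNAR) with missing at random (MAR), and claim no robustness to MNAR from this analysis.
   - (b) Keep MNAR and specify it. After imputation under MAR, add a pre-set shift, for example 0, 10, 20 and 30 points, to the imputed percent changes in the obicetrapib arms (30 removes the planned effect). Report the Rubin-pooled estimate and confidence interval at each shift.
2. Add treatment to the prose list of imputation variables and treat it as categorical in both steps: by arm or with two indicator variables in the MCMC step, and with a CLASS statement (or by arm) in the monotone step. Make the example code match.

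Cost: option (a) is a change of label plus one added variable. Option (b) adds a few lines of SAS and gives a slightly less favourable sensitivity estimate, about -28.5 instead of -30 at 5% missing with full loss of effect. Neither needs new data or participants.

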5.2 Rationale for Dosing

In previous clinical studies of obicetrapib in healthy volunteers and patients, near maximal effects were observed at the 5 mg obicetrapib dose level with increased HDL-C levels and decreased LDL-C levels. A statistically significant reduction in Lp(a) levels from baseline was also observed at the 10 mg obicetrapib dose level. Therefore, the present study will utilize doses of 5 and 10 mg obicetrapib in participants currently receiving high-intensity statin therapy.

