#### 2.2.4 Sample Size Determination

A sample size of at least 108 evaluable participants (ie, 36 participants per treatment group) will provide >90% power to detect a 30% difference in LDL-C reduction at Day 56 (standard deviation of 15%) for each of the obicetrapib groups compared to the placebo group at a 2-sided significance level of 0.025.

The sample size for this study was determined in order to provide sufficient power for the analyses of the primary efficacy endpoint described above. Therefore, assuming an approximately 5% dropout rate, enrollment of approximately 114 participants (ie, 38 participants per treatment group) is planned for this study. This sample size will also contribute sufficient participant exposure and safety data.

Participants will be stratified according to their Screening Visit (Visit 1) LDL-C levels (≥100 or <100 mg/dL).

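### Sensitivity Analysis 1's example code imputes LDL-C with treatment as the number 0/1/2; if the dose response plateaus, this slightly shrinks the 5 mg effect and widens the dose gap

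*SAP*

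**What the plan says.** SAP 3.4.1, Sensitivity Analysis 1, imputes missing Day 28 and Day 56 LDL-C in two PROC MI steps, fits the MMRM to each completed data set and pools with Rubin's method.

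- **Coding.** The code notes define "TREATMENT = 0 (Placebo), 1 (5 mg obicetrapib), 2 (10 mg obicetrapib").
- **Step 1 (MCMC).** The call reads "var TREATMENT LDLC base LDLC Day28 LDL Day56; mcmc impute=monotone chain=multiple".
- **Step 2 (monotone regression).** The SAP says "In the second step, the remaining monotone missing values will be imputed", and this call has the same VAR list, run by imputation number only.
- **CLASS.** Within the imputation and pooling code, treatment is declared categorical only at pooling: "proc mianalyze parms(classvar=full)=mixLSM; class TREATMENT".
- **Text.** The prose does not name treatment: "The variables for the imputation model will consist of LDL-C values from Baseline and Days 28 and 56".
- **Reported contrasts.** "the difference of the adjusted treatment means (the two doses of obicetrapib therapy – Placebo) will be presented".

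On the expected dose response, Protocol 5.2 says "near maximal effects were observed at the 5 mg obicetrapib dose level". SAP 2.2.4 powers the trial for one 30% difference, SD 15%, "for each of the obicetrapib groups compared to the placebo group".

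**The concern.** A numeric 0/1/2 variable gets a single slope in the imputation model. Given the other variables, the step from placebo to 5 mg is forced to equal the step from 5 mg to 10 mg. The MMRM applied afterwards has no such constraint, so the imputation model is more restrictive than the analysis model. Where the response flattens after 5 mg, values imputed in the 5 mg arm show too little reduction, and those in the placebo and 10 mg arms show too much.

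A sensitivity analysis should differ from the primary result only because the missing-data assumption differs. Here part of any difference would come from how the arms were coded, and a reader could not separate the two. The distortion falls on the 5 mg estimate in a trial that Protocol 1.4 says will support dose selection. The prose and the code also disagree on whether treatment is in the imputation model at all.

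**Working it through.** **The plan's own figures.** With 36 per arm and SD 15, the standard error of a pairwise difference is 15 × √(2/36) = 3.54. Power for 30 points at two-sided 0.025 is Φ(30/3.54 − 2.24) = Φ(6.2), above 99.99%, so the stated >90% holds with a wide margin. Enrolment is 108/0.95 = 113.7, rounded up to 114, as stated.

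**What the numeric coding imposes.** Take arm means 0, −30, −30, which is the planning difference for each dose, at x = 0, 1, 2 with equal arms.

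- Slope = [(−1)(20) + (0)(−10) + (1)(−10)]/2 = −15, through the mean of −20 at x = 1.
- Fitted means are −5, −20, −35.
- In imputed values the 5 mg effect is −15 instead of −30, the 10 mg effect stays at −30, and the gap between doses is −15 instead of 0.

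**Expected contrast when a share m is missing at both visits:** (1 − m) × true + m × line.

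- m = 5%: 5 mg effect = 0.95 × (−30) + 0.05 × (−15) = −29.25; dose gap = 0.05 × (−15) = −0.75.
- m = 10%: −28.5 and −1.5.
- m = 20%: −27.0 and −3.0.

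**Simulation of step 2**, which is the step that fills a missing Day 56. It used 38 per arm and 1,000 trials. Assumptions not in the documents: baseline mean 95 and SD 20 mg/dL, Day 28 to Day 56 correlation 0.5 or 0.8, the same plateau at Day 28, and equal missingness in each arm. Bias of the 5 mg effect toward zero, in percentage points:

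| Missing per arm | Both visits missing | Day 28 observed |
|---|---|---|
| 5% (2 of 38) | 0.76 to 0.82 | 0.11 to 0.35 |
| 10% | 1.51 to 1.53 | 0.24 to 0.58 |
| 20% | 2.99 to 3.09 | 0.46 to 1.24 |

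The dose gap widens by about the same amounts. At 5% missing, the 10 mg effect moves by less than 0.1.

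**Large-sample check on the mg/dL scale** (baseline median 92 mg/dL, log-SD 0.25, also assumed). With both visits missing, imputed values are off by −4, +10 and −6 points in placebo, 5 mg and 10 mg. At 5% missing the 5 mg contrast shifts by 0.05 × 14 = 0.70 and the dose gap by 0.05 × (−16) = −0.80. With Day 28 observed, the 5 mg shift is 0.17 to 0.39 for visit correlations of 0.7 down to 0.3.

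**Relative size.** 0.39/3.54 = 0.11 standard errors and 0.80/3.54 = 0.23. Power at 29.25 points, or even 27, is still above 99.99%.

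**Shape dependence.** For a linear response (0, −15, −30) the fitted line passes through the true means and the bias is about zero. For (0, −30, −40) the 5 mg effect at 5% missing is −29.50, a shift of 0.5.

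**After the fix.** With two arm indicators the simulated bias at 5% missing, with both visits missing, is −0.09 (5 mg), −0.08 (10 mg) and 0.00 (dose gap), with Monte Carlo error 0.03. Imputing by arm gives zero in the large-sample check.

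**The case against.** - **Both visits missing is the less likely case.** This stands. Protocol 4.5 asks participants who stop early to attend an Early Termination Visit, Appendix A takes a lipid profile there, and SAP 3.1.2 assigns that visit to the first post-baseline window (analysis days 2 to 42) or the second (days 43 to 71). A dropout who attends by day 71 therefore supplies a Day 28 or Day 56 value, so the figures for an observed Day 28 should lead. The 10% and 20% rows are two and four times the planned dropout.
- **The plan does not forecast identical doses.** This stands in part. A difference the trial is powered to detect is not a prediction, and near maximal does not mean equal. The direction is conditional on a plateau, but that is the shape the documents point to.
- **The code is an example.** SAP section 6 leaves detailed programming to a separate document, and a CLASS line could have been lost when the code was read from PDF. Neither can be excluded. However, none shows in either PROC MI call, and this is the only imputation specification in the documents.
- **The quoted line is step 1.** With its monotone option, step 1 fills a missing Day 28 when Day 56 is present. The Day 56 distortion arises in step 2, which has the same variable list, so the fix must cover both.

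A reader might go further and infer two things that the documents do not support. One is that the error contaminates the primary result. Protocol 9.2.1.1 does call for multiple imputation, but SAP 3.4.1 performs none in the primary analysis, and the protocol contains no imputation code; that conflict is a separate matter. The other is that the analysis would report a false difference between 10 mg and 5 mg. The listed contrasts are each dose against placebo. The gap would be seen only by comparing the pooled arm results.

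**Conclusion.** The point holds as a minor error in the example code. As written, both imputation steps force equal dose steps, which the analysis model does not assume and the prose does not mention. Given a plateau, equal missingness across arms and the planned 5% missing, the 5 mg effect is pulled toward zero, and the apparent dose gap widened, by about 0.2 to 0.4 points when Day 28 is observed. The shift is nearer 0.1 if the visit correlation is as high as 0.8, and at most about 0.7 to 0.8 when both visits are missing. That is roughly 0.1 to 0.2 standard errors. With a linear response it is about zero.

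Neither comparison with placebo can be overturned. The case for correcting it is that the artefact is avoidable and would be indistinguishable from a real effect of the missing-data assumption. Baseline spread and visit correlation are assumed here, not taken from the documents.

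**What to change.** Either of two changes removes the dose-line constraint:

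1. Sort by treatment, run both PROC MI steps BY TREATMENT (the second also BY _Imputation_), and drop TREATMENT from both VAR lists. About 36 participants per arm is enough for a three-variable imputation model.
2. If one joint model is preferred, replace TREATMENT with two 0/1 arm indicators in both steps. Step 1 needs indicators rather than a CLASS statement because MCMC takes continuous variables only. The common slope across arms then leaves an error of roughly 1 point or less per imputed value, about 0.1 point in a contrast at 5% missing.

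In the Sensitivity Analysis 1 text, state that imputation is done by arm or that treatment enters as a categorical variable, so that prose and code agree. The cost is a few lines of SAS and one SAP sentence, with no change to trial conduct or data collection.

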#### 3.4.1 Primary Efficacy Endpoint

#### Primary Analysis

The primary efficacy endpoint is the percent change from Day 1 to Day 56 in LDL-C (as determined by approach 1) for each obicetrapib group compared to the placebo group. The percent change will be calculated from Baseline to each measurement taken at Day 28 and Day 56.

The percent change in LDL-C from Day 1 to Day 56 for each treatment is defined mathematically as  $\mu_j$ , where j stands for the jth treatment (j=0,1,2) and the subscript 0 refers to the placebo group. The hypotheses testing to the percent change in LDL-C from Day 1 to Day 56 is then defined statistically as following:

$$H_0$$
:  $\mu_i - \mu_0 = 0$ ,  $H_1$ :  $\mu_i - \mu_0 \neq 0$ , where  $j=1,2$ 

The primary efficacy analysis of the percent change from Day 1 to Day 56 in LDL-C will be performed using a mixed model for repeated measures (MMRM) approach. The analysis will include fixed effects for treatment, visit, and treatment-by-visit interaction, along with a covariate of the Baseline value as a continuous covariate. It is to note that randomization was stratified by categories of LDL-C value (≥100 or <100 mg/dL) only to ensure similar distribution of LDL-C values across all treatment. However, the MMRM model will include the original scale of the LDL-C value as a continuous covariate, not categorical.

The Restricted Maximum Likelihood estimation approach will be used with an unstructured covariance matrix. The least squares means, standard errors, and 2-sided 95% confidence intervals for each treatment group and for the pairwise comparisons of each dose of obicetrapib to the placebo group will be provided. Adjustment for multiple comparisons will be made using Dunnett's test in accordance with the power and sample size calculations utilized for the study.

The MMRM approach will include all available assessments of percent change in LDL-C from Baseline to Day 28 and Day 56. The model assumes the data are missing at random (MAR). If any data are missing, the model will use all information from the other time points to estimate the mean treatment difference at the given time point. No imputation of missing data will be performed for the primary efficacy endpoint analysis.

For participants who are withdrawn from the study because of the use of a prohibited medication, data occurring after the intercurrent event of prohibited medications use will be excluded from the

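### Sensitivity Analysis 1 pools its imputed results without a complete-data degrees of freedom, so its 95% intervals come out about 1.2% too narrow

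*SAP*

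**What the plan says.** The point concerns SAP section 3.4.1, Sensitivity Analysis 1, and nothing else. On the number of imputations the SAP says "Initially, 25 data sets will be imputed for non-monotone missing values in the original dataset". If more cases are incomplete than expected, "then the number of imputations will be increased for the final analysis".

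The MMRM is fitted to each completed data set, and the results are "combined using Rubin's method to construct the treatment estimates using the parameter estimates and associated standard errors". The dose-placebo difference "will be presented with the associated standard error and 95% confidence interval".

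The example SAS code pools twice: "proc mianalyze parms(classvar=full)=mixLSM" for the least squares means and "proc mianalyze parms(classvar=full)=mixDIFF" for the differences. Each call has only a CLASS, a MODELEFFECTS and an output statement besides the input data set. Neither has the EDF= option, and no SAP text names a small-sample df. The primary MMRM uses no imputation, so it is not affected.

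**The concern.** Rubin's classical df measures only how well the between-imputation variance is estimated. It treats the complete-data analysis as if it had infinite df. As missingness falls, the classical df therefore grows without limit, although the trial has only about 110 residual df. Imputed data cannot carry more df than complete data would.

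The practical result is that the pooled interval takes its critical value from an almost normal distribution instead of a t distribution on about 100 df. The error always goes in one direction, towards a narrower interval. What is at stake is the stated width of the intervals in one supportive analysis.

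**Working it through.** **Inputs from the documents**
- Imputations: m = 25 (SAP 3.4.1).
- Sample size: 114 randomised, 38 per group; 108 evaluable, 36 per group; about 5% dropout (SAP 2.2.4). These agree: 36/0.95 = 37.9, rounded up to 38, and 3 × 38 = 114.
- Planned effect: difference 30 points, SD 15 (SAP 2.2.4).
- Model: "include fixed effects for treatment, visit, and treatment-by-visit interaction, along with a covariate of the Baseline value as a continuous covariate". At Day 56 this amounts to three treatment means and one baseline slope, so complete-data df v0 = 114 − 4 = 110, or 108 − 4 = 104.

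The SAP states no df for the pooled analysis, so there is no figure of its own to reproduce.

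**Assumption.** Let λ = (1 + 1/m)B/T, the share of the pooled variance T that is due to missing data, where B is the between-imputation variance. The documents do not give λ. I take 2% to 10%, centred on the planned dropout.

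**Formulas**
- Classical Rubin: df_R = (m − 1)/λ².
- Observed-data df: df_obs = [(v0 + 1)/(v0 + 3)] × v0 × (1 − λ).
- Barnard-Rubin: df_BR = 1/(1/df_R + 1/df_obs).

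**Worked case, λ = 0.05, v0 = 110**
- df_R = 24/0.0025 = 9,600.
- df_obs = (111/113) × 110 × 0.95 = 102.65.
- df_BR = 1/(1/9,600 + 1/102.65) = 101.6.
- 97.5% t quantiles: 1.9602 on 9,600 df and 1.9836 on 101.6 df. The coded interval is 1 − 1.9602/1.9836 = 1.18% narrower.

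**Range, m = 25, v0 = 110**

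| λ | Classical df | Barnard-Rubin df | Small-sample interval wider by | Nominal coverage as coded |
|---|---|---|---|---|
| 0.02 | 60,000 | 105.7 | 1.16% | 94.7% |
| 0.05 | 9,600 | 101.6 | 1.19% | 94.7% |
| 0.10 | 2,400 | 93.5 | 1.26% | 94.7% |

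With v0 = 104 and λ = 0.05 the Barnard-Rubin df is 96.0 and the coded interval is 1.25% narrower. At λ = 0.20, beyond the assumed range, the classical df is 600, still far above 110.

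**More imputations do not help.** At λ = 0.10, going from m = 25 to m = 50 raises the classical df from 2,400 to 4,900.

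**Is λ near 5% plausible?** I simulated 114 participants with 5% of Day 56 values missing and 25 imputations. Median λ was 0.046 with an assumed Day 28 to Day 56 correlation of 0.6, and 0.056 with 0.3. Median classical df was about 11,400 and 7,600, and it exceeded 1,000 in over 98% of runs.

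**Size on the endpoint's scale.** With 36 per group the standard error is 15 × √(2/36) = 3.54 points. The half-width is 1.9602 × 3.5355 = 6.93 on 9,600 df and 1.9836 × 3.5355 = 7.01 on 101.6 df, a gap of 0.08 percentage points. The planned effect is 30/3.5355 = 8.5 standard errors.

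**The case against.** The best case against raising this is that it has no practical consequence. A half-width that moves by 0.08 points cannot change the reading of an effect of 8.5 standard errors, and the estimates and standard errors stay the same. That stands, and it limits the point to a minor one.

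The code is also labelled as an example, and SAP section 6 defers to separate programming specifications. That is fair, but the prose likewise names only estimates and standard errors, so nothing in the SAP tells a programmer to supply the df. It can also be said that classical df simply is Rubin's method. It is, but it is a large-sample formula, and this trial has about 110 df.

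The simulation does not show under-coverage. Simulated coverage as coded was 95.6% to 95.8%, with Monte Carlo error of about 0.7 points, which is too coarse to detect a shortfall of 0.3 points. The statement that the intervals are too narrow rests on comparing t quantiles.

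A reader might infer three stronger things, none of which the documents support:
- **That this makes the intervals not comparable with the primary MMRM intervals.** The MMRM example code was not available in the text reviewed, so its df method is unknown. The primary analysis also calls for Dunnett's adjustment, which Sensitivity Analysis 1 does not mention. If the primary intervals are adjusted, their critical value is about 2.24 (two comparisons, shared control, 110 df) against 1.98 unadjusted. That 13% gap is far larger than 1.2%, and EDF= would not close it.
- **That agreement between analyses, or an apparent gain in precision, is distorted.** Those are judged on estimates and standard errors, which do not depend on the df.
- **That p-values specified by the plan are wrong.** For this analysis the SAP promises estimates, standard errors and a 95% interval. It states a significance level only for Sensitivity Analysis 2.

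**Conclusion.** The point holds as a small, one-directional defect in the intervals of Sensitivity Analysis 1. Followed as written, the plan pools on 2,400 to 60,000 df where about 93.5 to 106 are justified, and the 95% intervals are about 1.2% to 1.3% too narrow across the two sample sizes considered. This rests on 2% to 10% missing information, 25 imputations and a complete-data df of about 110 (104 on 108 participants). No conclusion is expected to change at the planned effect. The change is worth making because it is simple and leaves the estimates and standard errors as they are.

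**What to change.** Add EDF= to both PROC MIANALYZE calls. Set it to the complete-data denominator df of the Day 56 contrast from the MMRM: about 110 for 114 participants, or 104 for 108. In the paragraph on Rubin's method, state that intervals use the Barnard-Rubin small-sample df, and carry the same instruction into the programming specifications.

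The cost is one option in two lines and one sentence of text. The downside is intervals about 1% wider. Data collection and trial conduct are not affected.
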